**Appendix B: Flow chart for enrollment, surveillance, and treatment of VTE in study subjects**

\* Major operative procedure, pelvic fracture, LE fracture, shock, spinal fracture, TBI (GCS<13), ISS>9, central line, BMI>30 and ~~preinjury~~ factors

### Appendix C: Caprini Risk Factor Assessment

From "Thrombosis Risk Assessment as a Guide to Quality Patient Care", [name], 2005. Available online at: [http://williams.medicine.wisc.edu/caprini\\_score.pdf](http://williams.medicine.wisc.edu/caprini_score.pdf)

EVANSTON  
NORTHWESTERN  
HEALTHCARE

#### Choose All That Apply

##### Each Risk Factor Represents 1 Point

- Age 41-60 years
- Minor surgery planned
- History of prior major surgery (< 1 month)
- Varicose veins
- History of inflammatory bowel disease
- Swollen legs (current)
- Obesity (BMI > 25)
- Acute myocardial infarction
- Congestive heart failure (< 1 month)
- Sepsis (< 1 month)
- Serious lung disease incl. pneumonia (< 1 month)
- Abnormal pulmonary function (COPD)
- Medical patient currently at bed rest
- Other risk factors \_\_\_\_\_

##### Each Risk Factor Represents 2 Points

- Age 60-74 years
- Arthroscopic surgery
- Malignancy (present or previous)
- Major surgery (> 45 minutes)
- Laparoscopic surgery (> 45 minutes)
- Patient confined to bed (> 72 hours)
- Immobilizing plaster cast (< 1 month)
- Central venous access

##### Each Risk Factor Represents 5 Points

- Elective major lower extremity arthroplasty
- Hip, pelvis or leg fracture (< 1 month)
- Stroke (< 1 month)
- Multiple trauma (< 1 month)
- Acute spinal cord injury (paralysis)(< 1 month)

##### Each Risk Factor Represents 3 Points

- Age over 75 years
- History of DVT/PE
- Family history of thrombosis\***
- Positive Factor V Leiden
- Positive Prothrombin 20210A
- Elevated serum homocysteine
- Positive lupus anticoagulant
- Elevated anticardiolipin antibodies
- Heparin-induced thrombocytopenia (HIT)
- Other congenital or acquired thrombophilia

If yes:

Type \_\_\_\_\_

\*most frequently missed risk factor

##### For Women Only (Each Represents 1 Point)

- Oral contraceptives or hormone replacement therapy
- Pregnancy or postpartum (<1 month)
- History of unexplained stillborn infant, recurrent spontaneous abortion ( $\geq 3$ ), premature birth with toxemia or growth-restricted infant

Total Risk Factor Score

#### **Appendix D: Risk Assessment Profile (RAP)**

Variable	Points
Underlying Condition	
Obesity	2
Malignancy	2
Abnormal Coagulation	2
History of Thromboembolism	3
Iatrogenic Factors	
Femoral Central Line >24 hrs	2
Transfusion, >4 units in 24 hrs	2
Surgery lasting >2 hrs	2
Repair or ligation of major vascular injury	3
Injury-related Factors	
Chest AIS > 2	2
Abdomen AIS >2	2
Head AIS > 2	2
Spinal Fracture	3
GCS <8 for >4 hrs	3
Complex lower extremity fracture	4
Pelvis fracture	4
Spinal Cord injury, paraplegia or quadriplegia	4
Age (yrs)	
≥40 but <60	2
≥60 but <75	3
≥75	4

## Appendix E: Definition of Major and Clinically Relevant Bleeding

**Table 1. Definition of Major and Clinically Relevant Bleeding.\***

### **Major bleeding**

- Bleeding associated with a fall in hemoglobin of 2 g per deciliter or more
- Bleeding that led to a transfusion of 2 or more units of packed red cells or whole blood†
- Bleeding that involved a critical organ (intracranial, intraocular, intraspinal, retroperitoneal, or pericardial)
- Bleeding that contributed to death

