**Methods/Procedures:**

This is a prospective, randomized study with outcomes determined by blinded event adjudication (PROBE). Patients will be screened upon admission to the hospital, and enrolled within 24 hours from admission. Subjects will then be randomized to either the surveillance arm or the no surveillance arm. Subjects enrolled in the surveillance arm will undergo bilateral DUS on post-injury days 1, 3, 7, and every 7 days thereafter until discharge from the hospital. Subjects in the no surveillance arm will have routine hospital care on the trauma service, with no DUS performed unless symptomatic for DVT. (See Appendix B) Trauma physicians and advanced practice clinicians (APCs) will perform daily history and physical examinations targeted at eliciting symptoms and signs of potential VTE in all subjects.

All subjects enrolled in both arms of the study will have appropriate VTE prophylaxis provided (enoxaparin 30mg SQ every 12 hours if BMI<30, enoxaparin 0.5mg/kg SQ every 12 hours if BMI>30) according to the current IMC trauma service guidelines. VTE chemoprophylaxis will be started upon admission, or when deemed clinically safe according to the trauma service protocols. If chemoprophylaxis is not begun right away (because of solid organ injury, traumatic brain injury, etc.), those subjects will receive mechanical prophylaxis according to the trauma service guidelines.

Asymptomatic DVT in the surveillance group will be determined on the day of the DUS, prior to hospital discharge. Symptomatic DVT and PE during hospitalization in both groups will be pursued using the Wells score as guidance for DVT diagnosis and using objective imaging as diagnostic confirmation. 90 day follow-up of all subjects will be performed by reviewing medical records in the Intermountain Healthcare computerized medical record to look for evidence of VTE. All outcomes will be adjudicated by a panel of independent physician adjudicators blinded as to whether the patients were randomized to surveillance or not.

All subjects diagnosed with acute proximal DVT or PE will be treated with therapeutic doses of anticoagulants while in the hospital and after discharge, as appropriate. Subjects who are diagnosed with isolated calf DVT while in the hospital will have a follow up DUS on day 14 after

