**Data Collection:**

[figure not shown]
The following variables will be collected for all subjects in both arms of the study in a secure, computerized database (REDcap):

1. Patient demographics
2. Past medical/surgical/family/social history
3. Mechanism of injury
4. Injuries sustained and Injury Severity Score (ISS)
5. All items in the Caprini DVT risk assessment model (See Appendix C)—this information will be used for descriptive purposes and as a means of comparing the two study groups.
6. All items in the Risk Assessment Profile (RAP) for VTE (See Appendix D)—this information will be used for descriptive purposes and as a means of comparing the two study groups.
7. VTE pharmacoprophylaxis agent, dose, time from admission to first dose, interruptions in pharmacoprophylaxis and for what reason
8. Mechanical prophylaxis modality used
9. Asymptomatic DVT in surveillance group with location
10. Symptomatic DVT/PE with location during hospitalization and at 90 days
11. DVT propagation with location during hospitalization and at 14 days
12. Major and clinically relevant bleeding during hospitalization and at 90 days (see Appendix E).
13. All cause mortality during hospitalization and at 90 days

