**Data Analysis/Statistics:**

A historic baseline incidence of the composite outcome of major bleeding events plus proximal DVT on the trauma service is about 5.5%. We expect that in the no surveillance group, the incidence of the composite outcome will be higher. We are not entirely sure how much higher, which is one of the reasons for performing this vanguard trial. The below power analysis reflects that. Based on this power analysis, we would need to enroll at least 1000 subjects in each arm to discern a true difference, perhaps more, depending on the difference in events between the two groups. It is unreasonable given current financial and time constraints to do this definitively at a single center.

Based on historical trauma service admissions of 3000 per year, we estimate that 65-75% of admitted patients will qualify for the study, and 50-75% of those will agree to enroll. Thus, we estimate that over the course of one year, we could enroll about 300 patients per arm. This number of patients should be sufficient to help us determine the feasibility of a definitive, likely multi-institutional future trial.

A chi-squared test will be calculated to compare the rate of VTE between the surveillance group and the no surveillance group

Effect Size	Minimum Sample Size per Group
6.5% (+1.0%)	Doesn't achieve 80% power at n=5000 per group
7.0% (+1.5%)	4,200
7.5% (+2.0%)	2,500
8.0% (+2.5%)	1,600
8.5% (+3.0%)	1,200
9.0% (+3.5%)	900
9.5% (+4.0%)	700
10.0% (+4.5%)	600

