### **Clinically relevant bleeding**

- Any bleeding compromising hemodynamics
- Any bleeding leading to hospitalization
- Subcutaneous hematoma larger than 25 cm^2, or 100 cm^2 if there was a traumatic cause
- Intramuscular hematoma documented by ultrasonography
- Epistaxis that lasted for more than 5 minutes, was repetitive (i.e., two or more episodes of bleeding more extensive than spots on a handkerchief within 24 hours), or led to an intervention (e.g., packing or electrocoagulation)
- Gingival bleeding occurring spontaneously (i.e., unrelated to eating or tooth brushing) or lasting for more than 5 minutes
- Hematuria that was macroscopic and was spontaneous or lasted for more than 24 hours after instrumentation (e.g., catheter placement or surgery) of the urogenital tract
- Macroscopic gastrointestinal hemorrhage, including at least one episode of melena or hematemesis, if clinically apparent with positive results on a fecal occult-blood test
- Rectal blood loss, if more than a few spots on toilet paper
- Hemoptysis, if more than a few speckles in the sputum and not occurring within the context of pulmonary embolism
- Any other bleeding type considered to have clinical consequences for a patient — such as medical intervention, the need for unscheduled contact (visit or telephone call) with a physician, or temporary cessation of a study drug — or associated with pain or impairment of activities of daily life

\* Any one or more of the criteria met the definition of either major or clinically relevant bleeding.

† A red-cell unit was defined as the quantity of red cells obtained from or corresponding to approximately 500 ml of whole blood.

---

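### The bleeding definition and its window do not exclude presenting-injury bleeding that occurs in hospital before randomization

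*Combined protocol and SAP*

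**What the plan says.** Item 12 of Data Collection lists "Major and clinically relevant bleeding during hospitalization and at 90 days (see Appendix E"). That window opens with the hospital stay, not with randomization.

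Methods/Procedures states: "Patients will be screened upon admission to the hospital, and enrolled within 24 hours from admission". Randomization comes after enrollment, and no separate time limit is set for it.

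The major list in Appendix E includes "Bleeding associated with a fall in hemoglobin of 2 g per deciliter or more", a transfusion of at least two units, and "Bleeding that involved a critical organ (intracranial, intraocular, intraspinal, retroperitoneal, or pericardial"). One criterion is enough. The clinically relevant list includes "Any bleeding compromising hemodynamics" and bleeding that results in hospital admission. The appendix mentions a traumatic cause only once, to raise the size threshold for a subcutaneous hematoma.

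Data Analysis/Statistics uses major bleeding in its planning composite: "A historic baseline incidence of the composite outcome of major bleeding events plus proximal DVT on the trauma service is about 5.5" percent. On the expected increase without surveillance it says: "We are not entirely sure how much higher, which is one of the reasons for performing this vanguard trial". The only test it names is a chi-squared test on VTE.

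**The concern.** Everyone enrolled is a trauma patient admitted within 24 hours of injury, and hemorrhagic shock is itself a qualifying factor in Appendix A. Some patients will therefore be bleeding from the presenting injury between arrival and randomization. Appendix E is credited to a VTE treatment study and refers to a study drug, which this trial does not have. It does not appear to have been adapted to acute trauma.

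A literal adjudicator would count an intracranial or retroperitoneal injury bleed in the emergency phase, or two units given for it, as a major bleeding outcome. Surveillance cannot influence such an event. At stake are the bleeding comparison and the composite rate, which a definitive trial would take as a planning input.

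**Working it through.** **1. Reading the passages together.** The window starts at hospitalization, and randomization can follow by about 24 hours. Appendix E gives no onset time, reference hemoglobin or rule on cause. Methods/Procedures gives the blinded panel no rule for setting injury bleeding aside. Bleeding that ended before arrival is outside the window; in-hospital bleeding before randomization is inside it.

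**2. The plan's own figures.** Inputs from Data Analysis/Statistics: 5.5% baseline, 80% power. The plan states neither alpha nor sidedness; I assume two-sided 5%. The pooled two-proportion formula is

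n = [1.960·√(2p̄(1−p̄)) + 0.842·√(p₁(1−p₁)+p₂(1−p₂))]² / (p₂−p₁)².

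For 5.5% versus 8.5% it gives 1,135 per arm, or 1,201 with continuity correction; the plan states 1,200. Every row from 7.0% to 10.0% is matched within 3% by at least one of the two variants. The 6.5% row needs 8,853, consistent with the plan's statement that 5,000 is not enough.

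**3. Break-even share.** Let b be the share of patients in each arm counted for bleeding before randomization, and r the true composite rate. With b independent of later risk, the observed rate is q = b + (1−b)r. For r = 5.5%, the b that yields an observed rate t is (t − 0.055)/0.945:

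- t = 6.5%: 0.010/0.945 = 1.06%, about 3 of 300
- t = 8.5%: 0.030/0.945 = 3.17%, about 10 of 300
- t = 10.0%: 0.045/0.945 = 4.76%, about 14 of 300

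This comparison assumes that the 5.5% excludes index bleeding. Both arms move together.

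**4. Difference, precision and sample size (illustration only; b is not in the documents).** The between-arm difference is multiplied by (1−b). The 95% half-width is 1.96·√(2q(1−q)/300), with both arms at the 5.5% level.

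| b | Observed rate for true 5.5% | A 3.0-point excess becomes | Half-width, 300 per arm | n per arm, 5.5% vs 8.5% |
|---|---|---|---|---|
| 0 | 5.5% | 3.00 | 3.65 points | 1,135 |
| 2% | 7.4% | 2.94 | 4.19 points | 1,466 |
| 5% | 10.2% | 2.85 | 4.85 points | 1,989 |
| 10% | 15.0% | 2.70 | 5.71 points | 2,937 |

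The sample size grows mainly because the variance rises with the rate, not because the difference shrinks.

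**5. Relaxing independence.** If those with index bleeding have k times the later risk of the others, with r fixed, q = b + (1−b)r/(1−b+bk). For k from 0 to 3, the break-even range runs from 1.0–4.5% to 1.2–5.3%. The need at b = 10% runs from 2,460 to 4,007 per arm. The multiplier on the difference at b = 10% then runs from 1 (k = 0) to 0.9/1.2 = 0.75 (k = 3).

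**The case against.** The strongest reply is that the plan is silent rather than wrong. Data Collection is a list of variables, and it uses the same time phrase for symptomatic VTE and for deaths, where it most naturally separates the hospital stay from 90-day follow-up. A historic composite of only 5.5% also hints that the authors did not mean to count injury bleeding. This stands as a limit: no sentence says that such bleeding counts, and a reader who infers an explicit counting rule goes too far. It does not close the gap. Methods/Procedures says outcome variables will be compared between groups, no section narrows the bleeding definition, and the basis of the 5.5% is not given.

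Other stronger readings also fail:

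- **Bias between arms.** Events before randomization should balance on average.
- **The hemodynamic and hospitalization criteria inflate the composite.** They belong to clinically relevant bleeding; the composite uses major bleeding only. Appendix A's shock factor overlaps the hemodynamic criterion, so that overlap reaches the composite only if a major criterion is also met.
- **The RAP contradicts the outcome.** The RAP item "Transfusion, >4 units in 24 hrs" can share a transfusion with the outcome, but the plan gives the RAP no baseline time point and uses it descriptively. That is overlap, not contradiction.
- **The expected excess is badly distorted.** The stated uncertainty is how much higher the no-surveillance arm will be. Under independence that excess shrinks only by (1−b).

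It is also fair that bleeding is absent from the research questions and the stated hypothesis, that the trial's declared product is feasibility, and that 300 per arm is imprecise even at b = 0.

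**Conclusion.** The gap is real and worth correcting, but it concerns the level and precision of the bleeding results, not the validity of the randomized comparison. Applied literally, the major criteria would count pre-randomization injury bleeding in both arms. If the 5.5% excludes such bleeding, a share of about 1% to 5% is enough to move an observed 5.5% to between 6.5% and 10.0%. At b = 5% the need for 5.5% versus 8.5% would be about 2,000 per arm instead of about 1,100.

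These sizes rest on an unknown b, on two-sided 5% testing and, for the headline figures, on independence of later risk. The documents cannot show how many patients are affected, because age over 40 or BMI over 30 alone also qualifies a patient. Nor can they show whether the 5.5% already leaves index bleeding out; until that is stated, the observed composite cannot be compared with it. The VTE test stands as planned.

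**What to change.** In Appendix E and item 12 of Data Collection:

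- Count as outcomes only bleeding whose onset, recurrence or worsening follows randomization.
- Judge the hemoglobin fall against the last value before randomization.
- Count only units given after randomization for such bleeding, so that both the bleeding event and the transfusion must be post-randomization.
- Exclude the index admission from the hospitalization criterion.
- Have the blinded panel already planned record onset time.

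In Data Analysis/Statistics, state which bleeding definition and window produced the 5.5%.

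Recording attribution to the presenting injury, and reporting rates with and without injury-attributed bleeding, are optional additions. If attribution is used, anticoagulant orders and ultrasound results should be masked in the bleeding packet where possible, because they may hint at the arm.

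The cost is a few sentences and one adjudication field, with no added patients or visits. The downside is some judgement about when injury bleeding has worsened.

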### **Clinically relevant bleeding**

- Any bleeding compromising hemodynamics
- Any bleeding leading to hospitalization
- Subcutaneous hematoma larger than 25 cm^2, or 100 cm^2 if there was a traumatic cause
- Intramuscular hematoma documented by ultrasonography
- Epistaxis that lasted for more than 5 minutes, was repetitive (i.e., two or more episodes of bleeding more extensive than spots on a handkerchief within 24 hours), or led to an intervention (e.g., packing or electrocoagulation)
- Gingival bleeding occurring spontaneously (i.e., unrelated to eating or tooth brushing) or lasting for more than 5 minutes
- Hematuria that was macroscopic and was spontaneous or lasted for more than 24 hours after instrumentation (e.g., catheter placement or surgery) of the urogenital tract
- Macroscopic gastrointestinal hemorrhage, including at least one episode of melena or hematemesis, if clinically apparent with positive results on a fecal occult-blood test
- Rectal blood loss, if more than a few spots on toilet paper
- Hemoptysis, if more than a few speckles in the sputum and not occurring within the context of pulmonary embolism
- Any other bleeding type considered to have clinical consequences for a patient — such as medical intervention, the need for unscheduled contact (visit or telephone call) with a physician, or temporary cessation of a study drug — or associated with pain or impairment of activities of daily life

\* Any one or more of the criteria met the definition of either major or clinically relevant bleeding.

† A red-cell unit was defined as the quantity of red cells obtained from or corresponding to approximately 500 ml of whole blood.

---

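### Appendix E counts any intramuscular hematoma shown on ultrasound as a clinically relevant bleed, but only the surveillance arm has routine leg scans, so detection alone can inflate non-major bleeding there

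*Combined protocol and SAP*

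**What the plan says.** Four parts of the Combined protocol and SAP bear on this.

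- **Appendix E, clinically relevant bleeding.** One item is "Intramuscular hematoma documented by ultrasonography". It carries no size limit, symptom requirement, new-onset requirement or condition on why the scan was done. The footnote makes any single criterion sufficient. The neighbouring subcutaneous hematoma item does have an area threshold, raised "if there was a traumatic cause". A catch-all item also admits other bleeding with clinical consequences, or bleeding "associated with pain or impairment of activities of daily life".
- **Methods/Procedures, imaging.** Surveillance subjects "will undergo bilateral DUS on post-injury days 1, 3, 7, and every 7 days thereafter until discharge from the hospital". The other arm has routine care "with no DUS performed unless symptomatic for DVT". One further scan can occur in either arm: "Subjects who are diagnosed with isolated calf DVT while in the hospital will have a follow up DUS on day 14 after" the initial diagnosis.
- **Data Collection, item 12.** The data collected in both arms include "Major and clinically relevant bleeding during hospitalization and at 90 days". Methods/Procedures says that outcome variables will be compared between the arms, and that outcomes are adjudicated blind to arm.
- **Data Analysis/Statistics.** The 5.5% baseline and the sample-size table concern major bleeding plus proximal DVT. The only named test is a chi-squared test on VTE.

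**The concern.** The randomized intervention is the same test that satisfies this bleeding criterion. If a silent leg hematoma is equally common in both arms, the surveillance arm has repeated chances to have it documented. The control arm has a chance only when DVT symptoms prompt a scan, or when an isolated calf DVT leads to the day-14 scan. The count can then differ between arms although the bleeding does not.

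The population makes such hematomas plausible. Appendix A lists lower extremity fracture, pelvic fracture and major operations among the qualifying factors. The definition is credited to a drug trial and still mentions pausing a study drug, although no drug is randomized here; it appears not to have been adapted.

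The protocol already handles the parallel problem for DVT: Data Collection records asymptomatic DVT (item 9) apart from symptomatic DVT/PE (item 10). Bleeding has no such separation.

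At stake is a misleading safety contrast in a vanguard trial meant to inform a larger one, and a definition that could be carried forward into that trial.

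**Working it through.** **The plan's own figures.** The only power calculation is the sample-size table. Its type I error is not stated; I assume 0.05 two-sided, with 80% power and 1:1 allocation. For 5.5% versus 8.5%, the pooled formula gives

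n = [1.96·√(2·0.07·0.93) + 0.8416·√(0.055·0.945 + 0.085·0.915)]² / 0.03² ≈ 1,135 per group, or 1,201 with continuity correction, against 1,200 in the table.

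Every stated size from 7.0% to 10.0% gives 80.5% to 83.1% power by the pooled formula. The table is sound and does not involve the hematoma item.

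**Difference in imaging.** A 14-day stay (assumed; the documents give no length of stay) brings scheduled scans on days 1, 3, 7 and 14: four in the surveillance arm and none in the other.

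**Size of the artefact.** The documents give none of these inputs, so all are assumptions except the 300 per arm from Data Analysis/Statistics:

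- b: rate of other clinically relevant bleeding, equal in both arms, set at 5%
- h: true prevalence of a leg intramuscular hematoma that no other item would count, equal in both arms
- s: probability that ultrasound documents such a hematoma, which differs by arm

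Arm rate = 1 − (1 − b)(1 − h·s), so the spurious difference is (1 − b)·h·(s_surv − s_ctrl).

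Worked case, h = 5%, s = 0.8 versus 0.1:

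- surveillance: 1 − 0.95 × 0.96 = 8.80%
- control: 1 − 0.95 × 0.995 = 5.475%
- extra patients: 300 × 0.03325 ≈ 10.0
- chance of p < 0.05 in that direction: Φ[(0.03325 − 1.96 × 0.02102)/0.02098] = Φ(−0.379) ≈ 35%

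With no artefact, that chance would be 2.5%.

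| s (surv / ctrl) | h | Surveillance | Control | Extra patients per 300 | Ratio | Chance of p < 0.05 |
|---|---|---|---|---|---|---|
| 0.2 / 0.1 | 1% | 5.19% | 5.10% | 0.3 | 1.02 | 2.8% |
| 0.2 / 0.1 | 5% | 5.95% | 5.48% | 1.4 | 1.09 | 4.4% |
| 0.2 / 0.1 | 10% | 6.90% | 5.95% | 2.9 | 1.16 | 6.9% |
| 0.8 / 0.1 | 1% | 5.76% | 5.10% | 2.0 | 1.13 | 5.5% |
| 0.8 / 0.1 | 5% | 8.80% | 5.48% | 10.0 | 1.61 | 35% |
| 0.8 / 0.1 | 10% | 12.60% | 5.95% | 20.0 | 2.12 | 80% |
| 1.0 / 0.0 | 10% | 14.50% | 5.00% | 28.5 | 2.90 | 98% |

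The choice of b matters little. At h = 10% and s = 0.8 versus 0.1, b = 3% gives 20.4 extra patients and b = 10% gives 18.9. The driver is h·(s_surv − s_ctrl). Its sign is fixed so long as surveillance documents more, and it tends to zero if reports seldom mention muscle.

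**After the fix.** If the hematomas that count are found by the same rule in both arms, s_surv = s_ctrl and the difference in this model is 0.

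**The case against.** The strongest reply is that the affected category is narrow and the effect may be negligible. Most of this stands.

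- **Scope.** A reader might infer that the trial's bleeding outcome as a whole is inflated. The documents do not support that. The item sits in the clinically relevant list only. No major criterion in Appendix E (hemoglobin fall, transfusion, critical organ, death) is met by an ultrasound finding on its own. The Significance and Benefits sections speak of major bleeding, so they do not show that this component is the safety comparison the protocol stresses.
- **Size.** A reader might also infer that inflation is certain. It is not: the documents give no hematoma rate and no reporting rule for muscle findings. The only scan finding listed specifically for the surveillance group is asymptomatic DVT with location.
- **Controls are not without routes.** They have symptom-driven scans and may have the day-14 scan. Painful or disabling hematomas count in either arm through the catch-all item. Only silent or incidental ones can differ.
- **Exposure varies.** Age over 40 or BMI over 30 alone qualifies a patient, so many subjects may have no leg or pelvic injury, and short stays mean few scans.
- **Use of the result.** No stated go/no-go rule depends on clinically relevant bleeding.

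Blinded adjudication is not an answer. Adjudicators judge only what was found, a hematoma on a routine scan is real and meets the definition, and its manner of discovery may reveal the arm. Nothing else in the plan equalises ascertainment.

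**Conclusion.** The point holds in limited form. Followed as written, the plan allows silent or incidental leg hematomas to be counted mainly in the surveillance arm, which can raise non-major clinically relevant bleeding there at equal true bleeding.

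The size cannot be computed from the documents. At 300 per arm and under the assumed inputs, it runs from under 1 to about 20 or more extra patients, and it is near zero if DUS reports rarely record muscle findings.

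Nor should any observed bleeding difference be read as detection alone. Treating scan-detected DVT with anticoagulants could cause real bleeding, and the plan gives no means of separating the two. That is a further reason to record why each scan was done. The change is worth making because it is cheap and the direction of the bias is predictable, not because a large effect has been shown.

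**What to change.** Add an ascertainment rule for this trial to Appendix E:

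- For the between-arm comparison, an intramuscular hematoma counts only if it was clinically suspected before the imaging that showed it. The rule is the same in both arms.
- A hematoma first found on a scheduled DUS (surveillance, or day-14 follow-up of a calf DVT) does not count through this item. Nor does it count through the catch-all item merely because the scan found it.
- Such a hematoma still counts if it meets a major bleeding criterion or later becomes symptomatic.

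In REDCap, record whether each scan was scheduled or symptom-driven. In the report, list scheduled-scan hematomas separately by arm with any resulting change in treatment, present major bleeding separately, and give a sensitivity analysis using Appendix E as it now stands.

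The cost is a short addition to Appendix E, one database field, a listing and one extra analysis. It changes how outcomes are counted, not patient care. The downside is that some real hematomas found only by surveillance, including a few that changed treatment, leave the main comparison and appear only in the listing and the sensitivity analysis. Prior clinical suspicion is also judged by staff who know the arm, so it should be documented before the scan result is available.
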